6.1.4. Hospital Discharge

Hospital discharge is defined as the day a hospitalized subject is discharged. Hospital Discharge visit should be performed if a hospitalized subject is discharged on any day other than a scheduled study visit day.

Subjects who were treated in the Phase 1 portion of the study may be discharged on the day following the final planned CYNK-001 infusion (i.e., discharged on Study Day 8, where infusions occur on Days 1, 4, and 7 or discharged on Study Day 5 if only two doses were received on Days 1 and 4.)

As part of discharge criteria, the study team should assess for further monitoring of subjects who may be experiencing toxicity of Grade 3 and above (either related or unrelated to CYNK-001) at the time of discharge and consult with the treating physician and clinical site study team. The decision to discharge a subject should be in consultation with the treating physician. Physicians should follow best clinical practice to determine appropriate timing of hospital discharge.

Upon discharge, plans should be made for appropriately delegated staff to have telephone contact with subjects every day between hospital discharge through at least Day 15 visit for safety/AE monitoring. The discharge plan should include follow-up visit schedule as well as planned telehealth visit schedule.

Upon discharge, subjects will be provided with a thermometer, pulse oximeter, and blood pressure monitor for at home collection of temperature, oxygen saturation, and blood pressure with written instructions on their use as well as expectations for self-monitoring. These daily measurements will be reported via telephone to the clinical staff during each daily telehealth visit. During these daily telehealth visits, subjects are to report any new symptoms or worsening of symptoms associated with previously identified adverse events and will also provide the study team with daily vital sign measurements. Any vital signs outside of normal range will be escalated to the clinical site study team and evaluated for appropriate management.

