6.9. Efficacy Endpoint Definitions

- **Time to Clinical Improvement by OSCI**: defined as the time from the date of randomization to the first date of clinical improvement measured by OSCI. (Appendix D). Clinical improvement is defined as an improvement at least by cross category (or Patient State improvement in Appendix D table, such as from Hospitalized Severe Disease to Hospitalized Mild Disease). Subjects who do not have clinical improvement on or before Study Day 28 will be censored at Study Day 28.
- **Clinical Status by OSCI**: defined by the Ordinal Scale score of 0 to 8 by OSCI (Appendix D).
- **Rate of Clinical Improvement by OSCI**: defined as the proportion of subjects who achieved clinical improvement by OSCI.
- **Time to Clearance of SARS-CoV-2**: defined as the time from the date of randomization to the clearance of SARS-CoV-2 by rRT-PCR by two negative results at least 24 hours apart, with the first negative as the start date of clearance. Specimens included are nasopharyngeal swab and oropharyngeal swab (if available). Subjects who do not have clearance on or before Day 28 will be censored at Day 28.
- **Rate of Clearance of SARS-CoV-2**: defined as the proportion of subjects with “negative” measurement of COVID-19 by rRT-PCR.
- **Time to Clinical Improvement by NEWS2**: defined as the time from the date of randomization to the first date of clinical improvement. Clinical improvement is defined as improvement of clinical symptoms as measured by the NEWS2 Score (Appendix C). Subjects who do not have clinical improvement on or before Study Day 28 will be censored at Study Day 28.
- **Rate of Clinical Improvement by NEWS2**: defined as the proportion of subjects who achieved clinical improvement.
- **Time to Pulmonary Clearance**: defined as the time of randomization to the date of pulmonary clearance. This is defined as disappearance of virus from LRT- specimen where it has previously been found (induced sputum if available, endotracheal aspirate if available). Subjects who do not have pulmonary clearance on or before Study Day 28 will be censored at Study Day 28.
- **Pulmonary Clearance Rate**: defined as the proportion of subjects who achieve pulmonary clearance.

- **Duration of Hospitalization:** defined as date of randomization to the date of medical discharge. Subjects who are not discharged on or before Study Day 28 will be censored at Study Day 28.

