13.1 Primary Efficacy Endpoint

13.1.1 Primary Efficacy Endpoint for Phase I

The efficacy analysis for Phase I will be based on the safety analysis population.

The primary efficacy endpoint for Phase I is clinical improvement by OSCI on or prior to Day 15. Clinical improvement by OSCI is defined as at least one patient state improvement compared to baseline. If clinical improvement by OSCI is demonstrated for at least 2 out of 14 subjects on or prior to Study Day 15, and CYNK-001 is deemed to be safe, the study will move to Phase II. Otherwise, the study will be terminated.

Phase I efficacy data will be summarized by descriptive analyses for the number and proportion of subjects who achieved clinical improvement by OSCI by Day 15.

The proportion of the clinical improvement by OSCI at Day 15 will be summarized with a point estimate, standard error and a 95% confidence interval.

Patients who do not achieve at least one patient state improvement will be considered as failure to improve by OSCI. No formal hypothesis testing will be carried out for this part of the analysis.

Subject listings of clinical status using OSCI will be provided.

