13.2 Efficacy Endpoints

The study includes the following efficacy endpoints:

- 1) Clinical status by OSCI at Day 28.
- 2) Clinical improvement by OSCI by Day 15.
- 3) Rate of clinical improvement by OSCI at Day 28. The rate is defined as the proportion of subjects who achieved clinical improvement by OSCI on or prior to Day 28.
- 4) Time to clinical improvement as measured by OSCI.
- 5) Time to clinical improvement by NEWS2. Time to clinical improvement by NEWS2 is defined as the time from the date of randomization (date of first dose of CYNK-001 for Phase 1) to the first date of clinical improvement by NEWS2. Clinical improvement by NEWS2 is defined as a 25% decrease compared to baseline in the NEWS2 Score. Subjects without clinical improvement by NEWS2 on or before Day 28 will be censored at Day 28.

- 6) Rate of clinical improvement by NEWS2 at Day 28. The rate is defined as the proportion of subjects who achieved clinical symptom improvement by NEWS2 Score on or prior to Day 28.
- 7) Rate of clearance of SARS-CoV-2 from mucosal specimens at Day 28. Rate is defined as the proportion of subjects with clearance of SARS-CoV-2 by rRT-PCR by two negative results at least 24 hours apart. Specimens included are nasopharyngeal swab and optional oropharyngeal swab.
- 8) Time to clearance of SARS-CoV-2 from mucosal specimens at Day 28. Clearance is defined as the time from the date of randomization to clearance of SARS-CoV-2 by rRT-PCR by two negative results at least 24 hours apart. Specimens included are nasopharyngeal swab and optional oropharyngeal swab.
- 9) Time to pulmonary clearance at Day 28. Clearance is defined as the time from randomization to the date of pulmonary clearance. This is defined as disappearance of virus from LRT specimen where it has previously been found (induced sputum and endotracheal aspirate if available).
- 10) Rate of pulmonary clearance at Day 28. Rate is defined as the proportion of subjects who had disappearance of virus from LRT specimens where it has previously been found.
- 11) Duration of hospitalization from date of hospitalization to date of medical discharge.
- 12) For subjects requiring supplemental oxygen, the days with supplemental oxygen-free up to Day 28.
- 13) Proportion of subjects who need invasive or non-invasive ventilation up to Day 28.
- 14) SOFA score for subjects admitted to the ICU from ICU admission to ICU discharge, up to Day 28.

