- Duration of hospitalization (from time from hospitalization to medical discharge up to Day 28)

The Kaplan-Meier method will be used for estimating the survival curves, the median survival time and its two-sided 95% confidence interval will be estimated. [REDACTED]

[REDACTED]

Mortality rate will be provided and be compared using Fisher's Exact Test.

For the endpoint of proportion of subjects who achieved clinical symptom improvement by NEWS2 Score by Day 28, clinical improvement is defined as a 25% reduction in NEWS2 Score. The proportions

and their two-sided 95% CIs will be calculated. Fisher's exact test will be used to test the difference between groups. If the subject has no data after baseline, the subject will be considered as failure in the analysis.

1) Calculation

- a. Respiratory rate, oxygen saturation, temperature, systolic blood pressure, and heart rate will be collected on the Vital Signs and Oxygen Saturation eCRF forms.
- b. Consciousness score will be based on the Physical Exam eCRF form. If Neurological is normal, then NEWS2 Consciousness will be scored as zero. If Neurological is abnormal, then the score will be determined based on the comments. A clinical review of the comments from the abnormal neurological findings will be required.
- c. Air or Oxygen will be based on the eCRF form Prior and Concomitant Procedure and Surgeries. If a subject had Preferred Term "Oxygen Therapy" then the NEWS2 Air or Oxygen Score will be 2 for the days from the start day through the end day of the procedure.
- d. Calculation of overall NEWS2 Score for a given day will be the sum of the scores from respiratory rate, oxygen saturation, temperature, systolic blood pressure, heart rate, consciousness, and air or oxygen categories. For infusion days, data for Vital Signs and Oxygen Saturation are collected 3 separate times. For infusion days, a separate overall score will be calculated for each time the Vital Signs and Oxygen Saturation is collected, and the worst overall score will be used as the NEWS2 Score for that day.

2) Missing data handling:

- a. If a measure for vital signs and oxygen saturation is missing, corresponding NEWS2 score will be set as missing, and the overall NEWS2 score takes the form $\geq xx$. If all categories from vital signs and oxygen saturation is missing, the overall NEWS2 score will be set as missing.

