14.7 Infectious Symptom Assessment

The infectious symptom assessment will be tabulated over time with the proportion of clinical status assessment as defined in the CRF. The descriptive statistics, including the proportion and its 95% confidence interval will be provided.

No missing data will be imputed for this part of analysis nor formal hypothesis testing will be performed.

Subject level listing of AEs, vital signs, laboratory assessments and inflammation assessments will be provided.

15. Changes in Conduct or Planned Analyses from the Protocol

Description of change of conduct: Early termination of the study by the company.

In review of the current status and enrolment challenges of the CYNK-001-COVID-19 clinical trial and given the current landscape of the COVID-19 pandemic and the rollout COVID-19 vaccine, a decision by

Celularity has been made to close the CYNK-001-COVID-19 clinical trial. As a result of this early termination, only 7 patients were enrolled and dosed in the Phase I portion.

Due to this change, a brief clinical study report will be provided instead of a full CSR. Based on this change, only the following analysis will be provided for Phase I along with supporting listings:

- Summary of Subject disposition
- Summary of major protocol deviations
- Summary of demographics and baseline characteristics
- Analysis of time to clinical improvement by NEWS2 score
- Analysis of rRT-PCR tests and time to clearance of SARS-CoV-2 by rRT-PCR results (if enough data available)
- Analysis of SOFA scores (if enough data available)
- Summaries of adverse events
- List of deaths
- Summaries of laboratory results, shift from baseline and abnormal laboratory values
- Summaries of vitals signs, oxygen saturation and ECG and shifts from baseline
- Summary of abnormal post-baseline QTc results

16. Analysis of Concomitant Medication and Concomitant Procedure

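### The closing analysis of the 7 dosed Phase I subjects leaves out the OSCI summary, the SAP's Phase I primary efficacy endpoint, without giving a reason, and keeps NEWS2 with a late-documented cut-off and loose rules for missing items

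*SAP*

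**What the plan says.** **OSCI.** SAP 13.1.1 states: "The primary efficacy endpoint for Phase I is clinical improvement by OSCI on or prior to Day 15". Improvement means moving up at least one patient state from baseline. The section plans the count, the proportion with standard error and 95% confidence interval, and subject listings of OSCI status. The SAP's Study Summary also places OSCI among the Phase I primary endpoints. Protocol Section 11 has OSCI recorded every day, in hospital and by phone after discharge.

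**Closure.** SAP 15 reports that the sponsor ended the study because of slow enrolment, the state of the pandemic and the vaccine rollout, and that "only 7 patients were enrolled and dosed in the Phase I portion". A brief study report replaces the full one, and "only the following analysis will be provided for Phase I along with supporting listings". The list contains "Analysis of time to clinical improvement by NEWS2 score" without condition. It contains rRT-PCR clearance and SOFA if there are enough data. It contains no OSCI summary.

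**NEWS2.** Protocol 6.9 sets no threshold: "Clinical improvement is defined as improvement of clinical symptoms as measured by the NEWS2 Score". SAP 13.2 does: "Clinical improvement by NEWS2 is defined as a 25% decrease compared to baseline in the NEWS2 Score". SAP 13.3 handles missing components in three ways:

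- Vital sign or oxygen saturation missing: "corresponding NEWS2 score will be set as missing, and the overall NEWS2 score takes the form" ≥ xx.
- Neurological finding missing or not assessed: the consciousness item scores 0.
- Air or oxygen: derived from the presence of an oxygen therapy record, so never regarded as missing.

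**The concern.** Early closure explains a shorter report. It does not explain why the one efficacy result that the SAP calls primary for Phase I is absent while another clinical score is kept. OSCI was to be collected daily, so the data should exist, and the list shows that its authors had a conditional form of words for endpoints with thin data (rRT-PCR, SOFA). OSCI received neither a place nor a condition.

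The score that remains has two weaknesses. Its definition of improvement is documented only in a SAP that already knows of the closure, in an open-label study. And some of its missing-item rules can register improvement in a patient who has not changed. With 7 subjects, one misclassified subject moves a proportion by 1/7 = 14.3 percentage points. At stake is whether the report shows the planned efficacy result at all, and whether a reader can judge how firm the NEWS2 result is.

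**Working it through.** The plan states no power, alpha or precision for the closing analysis, so there is no figure of its own to reproduce. The check compares texts and then applies the scoring rules.

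**1. List against endpoint.** SAP 13.1.1 plans an OSCI count, proportion and interval. SAP 15 gives an exclusive list without them. SAP 13.1.1 also plans OSCI listings; SAP 15 allows supporting listings but does not say whether OSCI is among them.

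**2. Timing of the cut-off.** The protocol (Amendment 5.1, 4 February 2021) has no NEWS2 threshold. SAP Version 1.0 is dated 16 September 2021, says in its Section 1 that there is no previous approved version, and reports the closure in its Section 15. In these documents the 25% rule is therefore first seen after closure.

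**3. What OSCI could show with 7 subjects.** Exact (Clopper-Pearson) 95% limits:

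- 0/7: upper limit 1 − 0.025^(1/7) = 0.41, so 0 to 41%.
- 4/7: the 0.025 quantile of Beta(4, 4) and the 0.975 quantile of Beta(5, 3), so 18.4% to 90.1%.

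The go/no-go rule of at least 2 responders in 14 does not carry over. P(X ≥ 2) = 1 − (1−p)^n − np(1−p)^(n−1):

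| True rate p | n = 14 | n = 7 |
|---|---|---|
| 10% | 0.42 | 0.15 |
| 20% | 0.80 | 0.42 |
| 30% | 0.95 | 0.67 |

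The result is therefore descriptive only, but it can be reported.

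**4. NEWS2 threshold in points.** From a baseline total B, the smallest qualifying drop is 0.25 × B rounded up: 1 point for B = 1 to 4, 2 points for 5 to 8, 3 points for 9 to 12. At B = 0 a percentage decrease is undefined, and the SAP does not address this. If an item worth k points at baseline later counts as 0 and nothing else changes, the rule is met when k/B ≥ 0.25, that is B ≤ 4k: up to 8 for a 2-point item, up to 12 for a 3-point item. The endpoint is the first date of improvement and no confirmation is required, so one such day is enough.

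**5. The rules applied to an unchanged subject.** Using Appendix C: respiratory rate 21–24 (2 points), oxygen saturation 94–95% (1 point), on oxygen (2 points), so B = 5.

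- *Oxygen not recorded later:* total 3; (5 − 3)/5 = 40%. Counted as improved.
- *Neurological result missing later:* the consciousness scoring is not in the text available, so assume altered consciousness scores 3. Then B = 5 + 3 = 8, the later total is 5, and (8 − 5)/8 = 37.5%. Counted as improved. At B = 8 this needs an item worth at least 2 points; with 1 point it happens only up to B = 4.
- *Respiratory rate missing later:* total ≥ 3. The item scores 0 to 3, so the true total lies between 3 and 6, while a 25% fall from 5 needs 3.75 or less. The SAP does not say how a lower bound is judged. Improvement follows only if ≥ 3 is read as 3.

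**6. The reverse case.** If the same subject's oxygen is unrecorded at baseline, B is entered as 3. When oxygen later stops and the true total falls from 5 to 3, the recorded change is 3 to 3, or 0%, and a real 40% fall is missed.

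**The case against.** The strongest case against acting has several parts.

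- **OSCI's status.** Protocol Table 2 names only safety as the Phase I primary endpoint and calls OSCI a futility check, which is moot once the trial has closed. This has some force, but Protocol 5.1 includes efficacy in the Phase I primary objective, with OSCI defining it for the decision to proceed, and SAP 13.1.1 calls OSCI improvement the primary efficacy endpoint outright.
- **Listings may suffice.** With 7 subjects, a listing would show each OSCI course. True if one is provided, but SAP 15 does not name it, and a listing is not the planned summary with its interval.
- **Selective outcome reporting.** A reader might infer that OSCI was dropped because of its results and NEWS2 put in its place. The documents do not support that. SAP 15 discloses the reduced list openly, gives closure reasons unrelated to efficacy, and nowhere says that NEWS2 substitutes for OSCI.
- **A post hoc threshold.** A reader might infer that the 25% rule was chosen with the data in view. Only the absence of an earlier approved SAP is stated; an unapproved draft containing the rule cannot be excluded.
- **Home readings.** After discharge, "subjects will be provided with a thermometer, pulse oximeter, and blood pressure monitor for at home collection of temperature, oxygen saturation, and blood pressure"; respiratory rate is not among these. A reader might infer that home days yield understated NEWS2 totals. No section says that telephoned values enter the score. SAP 13.3 takes vital signs from the eCRF, and Protocol 12.1.4 includes respiratory rate and has vital signs after discharge collected at the outpatient facility.
- **Net bias towards improvement.** Some rules push the other way: the worst of the separate scores is used on infusion days (SAP 13.3), and the worst vital signs are recorded on other days with multiple readings (Protocol 12.1.4). Items missing at baseline also hide improvement. Protocol 12.1.7 asks for careful oxygen documentation, daily from admission to discharge, so gaps may be few.

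These objections limit the NEWS2 part to what the rules can do. They do not remove the omission of the OSCI summary.

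**Conclusion.** The point holds in a limited form. The closing list omits the summary of the endpoint that the SAP itself names as primary for Phase I efficacy, and gives no reason specific to it. The omission is disclosed but unexplained.

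For NEWS2, the 25% cut-off is first documented after closure. As written, the zero score for a missing neurological result and the never-missing oxygen item can produce apparent improvement when an item that scored at baseline is later unrecorded: a 40% fall in the oxygen example, and 37.5% in the neurological one under the assumed 3 points. The ≥ xx rule is an unspecified comparison; by itself it does not create improvement. Whether any of the 7 subjects is affected, and in which direction on balance, cannot be known from the documents.

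The inferential weight is small either way: 7 uncontrolled subjects, no hypothesis test, no remaining go/no-go decision. The case for change rests on completeness of reporting and on how little the change costs.

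**What to change.** 1. Add to the SAP 15 list the number and proportion of the 7 subjects with at least one Patient State improvement by Day 15, with an exact (Clopper-Pearson) 95% confidence interval. Name the OSCI subject listing from SAP 13.1.1 among the supporting listings. If the sponsor still prefers to omit the summary, state why.
2. Describe NEWS2 in the report as a supportive, non-primary Phase I endpoint. Calling it secondary would be inaccurate, because the protocol gives it that status only in Phase II. Disclose that the 25% cut-off is first documented in SAP Version 1.0, after closure.
3. Say how ≥ xx totals and a baseline of 0 are handled.
4. Add a sensitivity analysis in which a day with a ≥ xx total, or without a neurological or oxygen record, counts as improved only if the 25% fall holds whatever the missing item scored. In the respiratory rate example (baseline 5, later ≥ 3), the total could be as high as 6, so the day would not count. This needs a stated definition of a missing oxygen record, since the current rule cannot tell room air from no entry.

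The cost is one small table from data the protocol already collects, one sensitivity analysis on 7 subjects, and a few sentences of SAP text. The sensitivity analysis may leave few evaluable days if documentation is sparse, which would itself be worth reporting.

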16.1 Analysis of Prior and Concomitant Medication

Prior medicine is defined as the medication that was given prior to the day of the first dose

Concomitant Medicine is defined as medication which is given on or after the date of first dose.

Frequency summaries of prior and concomitant medications coded with WHO drug dictionary (version Mar2020) will be provided by treatment group.

At each level of subject summarization, a subject is counted once if the subject reported one or more medications. Complete listing, including reason for use, duration, frequency and dosage of concomitant and prior medication will be provided.

